All interactions (in person, over the phone) with subjects will be in a private room (i.e., room N414 of the Field House) and at a time when the subject is comfortable discussing screening questions. During data collection, we will only collect the minimum amount of information necessary to answer the research question.

X.2

Are you collecting the Social Security Number of any subjects for any purpose?

Yes

X.3

Provide the intended usage of SSN:

- To provide compensation to subjects

X.4

How will information/data be collected and stored for this study (check all that apply):

- Paper/hard copy records (hard copy surveys, questionnaires, case report forms, pictures, etc.) - Hard copy data will be stored in a locked file cabinet accessible only by research personnel. At night, the second story of the Health and Human Physiology Department is restricted to authorized key holders, and the room in which the file cabinet is located is restricted only to current laboratory staff.
- Electronic records (computer files, electronic databases, etc.) - All data collected, including personal identifiable information, will be stored electronically on University of Iowa secured networks (i.e., the rdss/Research Data shared drive) with access restricted to the current investigators.
 - Name - [name]
 - Title - IT Support Consultant
 - University Job Classification - Faculty/Staff
- Biologic samples (blood draws, check swabs, saliva samples, tissue samples, etc.) - Biologic samples (blood draws, check swabs, saliva samples, tissue samples, etc.) - Cru staff will draw blood, place a patient identifier label (zebra sticker) on the PST tube, place in a bio-hazard bag and hand deliver the specimen to UIDL staff. Specimens will be delivered by CRU personnel to Specimen Control (also known as Technical Services). Upon receipt, core lab personnel will accession the specimen into Epic. Please note that the core laboratory is staffed 24/7, 365 days a year and has restricted access. Specimens are processed and temporarily stored, securely, prior to testing. After the completion of testing, specimens are discarded as biological waste. All biological waste is eventually incinerated.
 - Name - [name]
 - Title - Clinical Professor
 - University Job Classification - Faculty/Staff

X.5

Do the confidentiality protections indicated above allow only members of the research team to access the data/specimens?

No

X.6

Describe

The data that will be shared with the Medical University of South Carolina (MUSC) will be de-identified, age, race and ethnicity will be reported as required by NIH (see attached template that will be requested for reporting purposes) as part of a final report to MUSC.

X.7

Does your study meet the NIH criteria for a Certificate of Confidentiality or will you be applying for Certificate of Confidentiality?

No

XI. Data Analysis

XI.1

Describe the analysis methods you will use, including, if applicable, the variables you will analyze

The generalized estimating equation (GEE) framework will be utilized to assess changes over time in fatigue and quality of life measures. An interaction term between time and treatment will allow us to test the within- and between-treatment differences over all time points. Using histograms, variable distributions will be assessed to decide which link function to specify when modeling each outcome. To account for the inherent correlation that occurs in repeated measures data, we will cluster on subject ID. In addition to

examining the unadjusted relationship between the time-treatment interaction and each outcome, we will consider the addition of control variables, which will reduce the likelihood of unaccounted confounders. The control variables being considered for inclusion in the adjusted models are age, sex, and disease duration. For each outcome, models will be fit for all possible combinations of control variables. The predictor set that yields the smallest Akaike information criterion (AIC) will be considered the optimal control variable set to adjust associations between the main predictor and the outcomes. Statistical significance will be assessed at the $\alpha = 0.05$ level.

XI.2

Provide the rationale or power analysis to support the number of subjects proposed to complete this study.

The sample size calculation was based on the Fatigue Severity Scale data from our own preliminary data that assessed the effects of multiple sessions of 4 mA tDCS on fatigue in people with multiple sclerosis. The effect size of this difference = 0.91 (Cohen's d). With alpha fixed at 0.05, we would need 20 total subjects in each group (tDCS and SHAM; details below) to achieve 80% power in a two-tailed independent samples test. Therefore, to account for 20% data and subject attrition, we will recruit 25 subjects per group (150 total).

XII. Future Research

XII.1

Do you wish to keep any information about subjects involved with this research project so that members of the current research team may contact them in the future for your own research projects?

Yes

XII.2

Do you wish to keep any information about subjects involved with this research project so that other researchers may contact them for future research?

Yes

XII.3

List the data or information you will keep:

Contact information and the outcome of the phone questionnaire.

XII.4

Does this project involve storing any data, tissues or specimens for future research?

Yes – contribution for future use is mandatory for participation in the study

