- *Physician services or services provided by non-physicians who are credentialed to bill (ARNPs, Physician Assistants, etc.)*

- Yes

V.25.b *Will there be any procedures or services that may happen as part of a subject's regular medical care and as part of the study?*

No

V.25.c *Will any study equipment or devices be supplied by a study sponsor?*

No

V.25.e *Is there or will there be an internal budget for this study?*

Yes

V.25.f *Is there or will there be an external budget for this study?*

No

V.26 *The study involves Department of Nursing Services and Patient Care nursing, nursing resources or evaluates nursing practices at UI Health Care.*

No

VI. Subjects

VI.1 *How many adult subjects do you expect to consent or enroll for this project?*
150

VI.2 *What is the age of the youngest adult subject?*
18.0

VI.3 *What is the age of the oldest adult subject?*
80.0

VI.4 *What is the percentage of adult male subjects?*
50

VI.5 *What is the percentage of adult female subjects?*
50

VI.6 *How many minor subjects do you expect to consent or enroll for this project?*
0

VI.13 *Describe EACH of your subject populations*

- *Include description of any control group(s)*
- *Specify the Inclusion/Exclusion criteria for EACH group*

Fifty post-acute COVID-19 men and women with enduring fatigue will be recruited into one of two groups (tDCS or sham, n = 25 in each group), 50 post-acute COVID-19 men and women without enduring fatigue will be recruited into one of two groups (tDCS or sham, n = 25 in each group), and 50 subjects with no history of a COVID-19 diagnosis (controls) will be recruited into one of two groups (tDCS or sham, n = 25 in each group). For the COVID-19 subjects (fatigue and without fatigue), only those that are discharged from the UIHC COVID-19 inpatient clinic and/or that meet the CDC guidelines for discontinuing home isolation (i.e., fever-free for at least 24 hours, all symptoms improved after 10 days) will initially be

considered as long as they meet the rest of the following criteria:

Inclusion criteria (COVID-19 fatigue subjects):

- 18–80 yrs.
- Previous positive COVID-19 test
- >30 days since positive COVID-19 diagnosis
- Meet CDC guidelines (<https://www.cdc.gov/coronavirus/2019-ncov/hcp/duration-isolation.html>) for discontinuation of home isolation
- Meet the criteria for fatigue, based on the Chalder Fatigue Scale CFQ-11 case definition of fatigue

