- *Participants will be told that the research includes completion of a particular task, when in fact, that task will not be administered.*
- *Study is designed to introduce a new procedure (or task) that participants are not initially told about.*
- *If yes, a waiver of informed consent must be requested under question IV.3.*

• No

VII.E. Project Description (E)

VII.E.1

Will subjects be randomized?

Yes

VII.E.1.a

Will any subjects be blinded to which study arm they have been assigned?

Yes

VII.E.1.b

Does the protocol permit telling subjects their treatment assignment at the end of the entire study?

Yes

VII.E.1.c

Describe the circumstances under which subjects will be told what study arm they have been assigned.

At the end of all sessions, and upon request by the subject, the participant will be informed about the stimulation condition they experienced.

VII.E.2

Describe randomization scheme/assignment including ratio such as 1:1, 2:1 etc.

The study will be a double-blind, sham-controlled, randomized parallel design. Post-COVID-19 patients with fatigue, post-COVID-19 patients without fatigue, and subjects without a history of a COVID-19 diagnosis (controls) will be randomly assigned to one of two groups. One group will

receive tDCS (tDCS Group; n = 25 in each group of subjects; 75 total) and the other group will receive SHAM (SHAM Group; n = 25 in each group of subjects; 75 total). The study will involve nine sessions at the INPL.

VII.E.3

Will any questionnaires, surveys, or written assessments be used to obtain data directly from subjects in this study?

Yes

VII.E.4

List all questionnaires, surveys, written assessments and ATTACH each one to the application.

(NOTE: You are NOT prohibited from attaching copyrighted materials to this application)

Chalder Fatigue Scale

C19-YRS-Covid-Rehab-screening-tool

Fatigue Assessment Scale (FAS)

Fatigue Severity Scale (FSS)

EQ-5D-5L Quality of Life questionnaire

Visual analog scale for pain

COVID19 Severity Survey

Pittsburgh Sleep Quality Index (PSQI) (to determine sleep quality)

International Physical Activity Questionnaire (IPAQ) (to quantify recent physical activity levels)

VII.E.5

Does this project involve creating any audiotapes, videotapes, or photographs?

No

VII.E.6

Provide a detailed description in sequential order of the study procedures following the consent process - DO NOT cut and paste from the Consent Document.

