Describe study populations separately if they will be participating in different procedures - include CONTROL population if applicable.

DESCRIBE:

- **What subjects will be asked to do/what happens in the study (in sequential order)**
- **The time period over which procedures will occur**
- **The time commitment for the subject for individual visits/procedures**
- **Long-term followup and how it occurs**

Symptomatic subjects will be asked to complete 7 lab study sessions. The first lab session will take approximately 3.5 hours, the fifth lab session will take approximately 2 hours, and the tDCS sessions will take approximately 30 minutes. In all, full participation will take approximately seven weeks, with three week breaks between Lab Sessions 5, 6, and 7. Asymptomatic subjects will be asked to complete 1 lab study session, lasting approximately 2 hours.

Vascular study: In the initial session (Day 1) all subjects will 1) be consented, 2) undergo a blood draw to evaluate interleukin-6 values, lipids, glucose and c-reactive protein, complete 3) pulse wave velocity testing (arterial stiffness); 4) carotid compliance/stiffness with ultrasound 5) brachial artery flow-mediated dilation (vascular endothelial function) 6) the Fatigue Assessment Scale (FAS), 7) the Fatigue Severity Scale (FSS), 8) the visual analog scale (VAS) for pain, 9) cognitive testing 10) 1-100 symptom scale, 11) international physical activity questionnaire (IPAQ), 12) Pittsburgh sleep quality index (PSQI), and 13) the 6-minute walk test. For asymptomatic participants, this will mark the end of their study participation. For symptomatic participants, they will then have their first round of the intervention receiving either sham or tDCS.

The following four days will include receiving either 20 min of tDCS or sham treatment, depending on group randomization. Day 5 will include the same testing battery (blood draw, PET scan in 10 subjects from each group [i.e., those that got the pre scan], questionnaires, fatigue testing, walking test) as Day 1, except the subjects will not repeat the MRI scan, strength testing, or receive tDCS.

LONG-TERM EFFECTS OF tDCS: Three- and six-weeks following Day 5, participants will repeat the testing battery conducted on Days 1 and 5.

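### VI.13 and VII.E.2 assign three populations to tDCS or sham (75 vs 75), but VII.E.6 stimulates only symptomatic participants; those labels are not mapped to the populations, and XI.1 names no analysis population.

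*Combined protocol and SAP*

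**What the plan says.** **Version A: three populations allocated.** VI.13 allocates each population to the two arms, 25 per cell. For the second one it says "50 post-acute COVID-19 men and women without enduring fatigue will be recruited into one of two groups (tDCS or sham", and never-COVID controls are treated in the same way. VII.E.2 repeats this: one arm is to "receive tDCS (tDCS Group; n = 25 in each group of subjects; 75 total) and the other group will receive SHAM", 75 in each. XI.2 does not itself randomise anyone, but its 25 per group and total of 150 match this layout.

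**Version B: only symptomatic participants stimulated.** VII.E.6 says "Symptomatic subjects will be asked to complete 7 lab study sessions" and "Asymptomatic subjects will be asked to complete 1 lab study session, lasting approximately 2 hours". After the Day 1 test battery it says "For asymptomatic participants, this will mark the end of their study participation", and then "For symptomatic participants, they will then have their first round of the intervention receiving either sham or tDCS". VII.E.19 pays the asymptomatic group for visit one only. VIII.1 confines the tDCS risks to symptomatic participants.

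**Session counts.** VII.E.2 says "The study will involve nine sessions at the INPL". VII.E.6 gives 7 or 1.

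**Controls.** The form prompt at VII.E.6 reads "Describe study populations separately if they will be participating in different procedures - include CONTROL population if applicable". The answer sorts people only as symptomatic or asymptomatic and does not say which of these controls are.

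**Analysis.** XI.1 specifies a GEE with a time-by-treatment interaction, clustered on subject, with age, sex and disease duration as candidate covariates. It has no population term and does not say which subjects enter the model.

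**The concern.** The two versions disagree on who is exposed to the intervention and who forms the randomised comparison. Each is repeated across several sections, so this is not a single slip, and VII.B.11 says that no separate written protocol exists to settle it.

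Two things are at stake. First, the stated number receiving each treatment may be wrong. If the non-fatigue subjects and controls are the asymptomatic ones, VII.E.2 would give 25 + 25 = 50 of them active stimulation, while VIII.1 treats the tDCS risks as not applying to them. Second, the analysis set is undefined. The model in XI.1 would mean something different depending on whether one-visit subjects, or stimulated subjects without fatigue, are pooled with the fatigue group. The aims in I.5 name only recovered COVID-19 patients, and no stated analysis uses subjects seen once.

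**Working it through.** **1. The plan's own sample size.** Inputs from XI.2: d = 0.91, two-sided alpha 0.05, 80% power, independent-samples test, 20% attrition.

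- Normal approximation: n = 2(1.960 + 0.842)² / 0.91² = 18.96, so 19 per arm.
- Noncentral t: n = 19.96, so 20 per arm, with power 80.1%. This reproduces the stated 20.
- Attrition: 20 / (1 − 0.20) = 25 per arm, as stated. Power with all 25 per arm observed is 88.3%.
- Total: 25 × 2 arms × 3 populations = 150, or 75 vs 75.

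The arithmetic is sound, and it sizes a single two-arm comparison.

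**2. How many are stimulated under each reading.**

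| Reading | Receive tDCS or sham | Seen once |
|---|---|---|
| VII.E.2 as written | 150 (75 vs 75) | 0 |
| VII.E.6; symptomatic = fatigue group, controls asymptomatic | 50 (25 vs 25) | 100 |
| VII.E.6; symptomatic = fatigue group, controls also stimulated | 100 (50 vs 50) | 50 |

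Equating symptomatic with the fatigue group is an inference. It rests on the recruitment sentence in VII.D.29, which contrasts people with continuing post-COVID fatigue with people who are asymptomatic. Placing controls in either column is an assumption. The 1–100 symptom scale in VII.E.6 lists many symptoms besides fatigue, so a non-fatigue COVID-19 subject could count as symptomatic. That would raise the stimulated count in the second or third row. VII.E.6 gives 75 vs 75 only if all 150 enrolled subjects go on to stimulation, in which case its asymptomatic category is empty.

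**3. Session counts.** VII.E.6 is consistent within itself: five daily sessions plus visits three and six weeks after Day 5 make 5 + 2 = 7. The nine in VII.E.2 matches neither 7 nor 1.

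**4. Effect on the model in XI.1.** A subject with only a baseline visit carries no information on change. Suppose all 150 were assigned an arm but only the fatigue group followed up. Each arm's baseline would then hold 75 subjects, of whom 50 (two thirds) come from populations absent at follow-up. A change within an arm would partly reflect who remained. With equal numbers per population in each arm, that shift is the same in expectation in both arms, so it falls mainly on the within-treatment differences that XI.1 also sets out to test. If all three populations were stimulated, the single interaction would average over subjects with and without fatigue, and disease duration has no value for never-COVID controls.

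**The case against.** The best reply is that the operational sections (VII.E.6, VII.E.19 and VIII.1) agree with one another, so staff following the visit schedule would know to stimulate only symptomatic participants. On that view the defect is design text in VI.13 and VII.E.2 that was not brought into line. This has force, and it is why it would go too far to say that staff face an impasse. It still leaves the stated arm sizes, the place of controls and the analysis population unresolved.

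Three stronger readings are tempting, and the documents do not support them.

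- A reader might infer that exactly 50 are randomised, one third of the 150. VII.E.6 states no number randomised, and the 50 needs both mappings in the second row of the table. VII.D.20 also screens for continuing problems with the C19-YRS, separately from the Chalder fatigue scale, so symptomatic need not mean fatigued. Nor does VII.E.6 say that asymptomatic subjects are unassigned; it says only that they leave before stimulation.
- A reader might infer that the trial is underpowered. The fatigue-group comparison keeps its 25 vs 25 under either version.
- A reader might infer that a GEE cannot accept one-visit subjects. It can, because clusters may be unequal. The problem is what those subjects would contribute.

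**Conclusion.** The contradiction stands and needs correcting. The stated 75 vs 75 receiving tDCS or sham is incompatible with the visit schedule as soon as any enrolled subject is asymptomatic. With symptomatic taken as the fatigue group, between 50 and 100 of the 150 are stimulated, depending on where controls belong; non-fatigue subjects with other symptoms would raise that range.

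Confidence is high for the contradiction, for the missing mapping and for the absence of an analysis population in XI.1. It is only moderate for any particular split, which depends on the assumptions stated above. This is an internal inconsistency, not an error in the sample-size calculation. Which version is right is for the sponsor to state.

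**What to change.** Reconcile VI.13, VII.E.2 and XI.2 with VII.E.6, VII.E.19 and VIII.1 on who is randomised and who is stimulated. Map the symptomatic and asymptomatic labels to the three populations, controls included. Reconcile nine sessions with 7 or 1. Then:

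- **If the one-visit schedule stands:** restate the randomised number in VI.13 and VII.E.2, and separate it from the 150 enrolled in XI.2. Restrict the time-by-treatment GEE in XI.1 to the randomised population. Describe the remaining subjects as non-randomised baseline comparators, with a stated cross-sectional comparison.
- **If all three populations are randomised:** estimate the treatment contrast within each population, by separate models or by population interactions. Separate models match the way XI.2 is sized; interactions at 25 per cell are not powered in the plan. Do not use disease duration as a covariate for never-COVID controls.

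Either way the cost includes rewording and an IRB modification, with no added subjects. The one-visit route gives a smaller headline randomised number. Treating all three populations means more visits, at 7 − 1 = 6 extra sessions for each subject now scheduled for one, and VII.E.6, VII.E.19 and VIII.1 would have to change as well.

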1-100 SYMPTOM SCALE: You will be asked to fill out a survey rating each of your COVID-19 symptoms individually on a scale from 0-100. Symptoms include chest pain, chills, diarrhea, dizziness/vertigo, dry cough, dry eyes, dry mouth, fatigue, fever over 100.3°F, headache, lack of appetite, loss of smell/taste, muscle or body aches, nasal congestion or runny nose, nausea or vomiting, shortness of breath, sore joints, and sore throat. These scores will be totaled and averaged for overall symptom severity.

PHYSICAL ACTIVITY: Participants will be asked to fill out short survey called the International physical activity questionnaire (IPAQ) to quantify job-related and leisure-time physical activity and sitting time over the past 7 days.

SLEEP QUALITY: Participants will fill out the Pittsburgh sleep quality index (PSQI) survey to determine sleep quality over the past month.

STRENGTH TESTING:

Knee extension/flexion will be performed in a sitting position. The range of motion will be between 100° and 0° of flexion. The axis for extension/flexion is assumed to be a horizontal line through the femoral condyles. The subject will be secured with Velcro bands to help isolate the knee joint. The isokinetic measurements will be performed with 3 maximal extension/flexion repetitions at 30°/s. In addition, three repetitions of isometric tests performed at 65° (extensors) and 30° (flexors) of knee flexion will also be obtained. All testing will be completed on both legs and the highest torque obtained from the three repetitions will be used to determine the weaker leg. The M1 that controls the weaker leg will serve as the anodal brain target for tDCS.

ISOKINETIC FATIGUE TEST: Subjects will perform 40 consecutive repetitions of isokinetic concentric/concentric flexion and extension of the knee on the stronger leg at 120°/sec. The weaker leg fatigue task will be completed in the same manner immediately after the stronger leg.

6 MINUTE WALK TEST (6MWT): The subjects will be led to a cordoned-off hallway to perform the walk. Subjects will be instructed to walk at their normal, usual pace back and forth between two points separated by 30 m for 6 min. Gait characteristics and distance walked will be calculated and recorded.

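### Leg fatigability is tested after maximal strength testing on Day 1 but without it on Day 5, so within-arm change from baseline is confounded with a change in prior effort

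*Combined protocol and SAP*

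**What the plan says.** All procedures are in VII.E.6 of the combined protocol and SAP.

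- **Strength test.** "The isokinetic measurements will be performed with 3 maximal extension/flexion repetitions at 30°/s", and "three repetitions of isometric tests performed at 65° (extensors) and 30° (flexors) of knee flexion will also be obtained". It is done on both legs, and "the highest torque obtained from the three repetitions will be used to determine the weaker leg".
- **Fatigue test.** The subject makes 40 consecutive flexion/extension repetitions at 120°/s, on the stronger leg first. Then: "The weaker leg fatigue task will be completed in the same manner immediately after the stronger leg".
- **Day 5.** The battery keeps the fatigue test ("questionnaires, fatigue testing, walking test) as Day 1") but drops the strength test: "except the subjects will not repeat the MRI scan, strength testing, or receive tDCS".
- **Follow-up.** "Three- and six-weeks following Day 5, participants will repeat the testing battery conducted on Days 1 and 5".

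No rest interval between strength and fatigue testing is given, and no fatigability index is defined. The numbered 13-item list for Day 1 contains neither the strength test nor the isokinetic fatigue test.

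Section I.5 names performance fatigability among the measures serving the objective. Section XI.1 plans a GEE with a time-by-treatment interaction, to test differences both within and between treatments.

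**The concern.** The fatigue test is meant to show whether the legs tire less after five sessions. That comparison needs the same conditions before each test. On Day 1 the same muscle groups have just made maximal efforts; on Day 5 they have not.

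Hypothesis 1 is worded as improvement after stimulation, and Hypothesis 2 carries that improvement to the follow-up visits. A reader of the results will therefore look at change from Day 1 in the tDCS arm, and XI.1 provides a test of it. If the lead-in affects the score, that test can be significant with no treatment effect, or can hide a real change. Visit and lead-in coincide completely between Day 1 and Day 5, so no later analysis can separate them.

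**Working it through.** **1. The plan's sample size, which supplies n.** XI.2 gives Cohen's d = 0.91 on the Fatigue Severity Scale, two-sided alpha 0.05 and 80% power. The normal approximation gives 2 × (1.960 + 0.842)² / 0.91² = 18.96, so 19 per group. The exact t calculation gives 19.96, so 20, with power 80.1%. Allowing for 20% attrition, 20 / 0.80 = 25, and 6 × 25 = 150. The plan's figures reproduce, and nothing here disputes them. They concern a questionnaire, not leg fatigability.

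**2. Order on Day 1.** The strength test determines which leg is weaker, and the fatigue test begins with the stronger leg. The ranking must be known first, so strength testing comes before fatigue testing on Day 1. This is an inference, but the plan's own logic requires it.

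**3. Amount of prior effort.** Per leg, on the natural reading:
- strength test: 3 × 2 isokinetic + 3 isometric extensor + 3 isometric flexor = 12 maximal contractions
- fatigue test: 40 × 2 = 80 contractions

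The ratio 12/80 = 15% is a ratio of counts only. Six of the 12 are isometric, and the other six are at 30°/s against 120°/s.

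**4. The visits side by side.**

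| Visit | Maximal strength test before fatigue test? |
|---|---|
| Day 1 | Yes (required by the leg ranking) |
| Day 5 | No (explicitly omitted) |
| 3 and 6 weeks | Not settled: the text points to Days 1 and 5, which differ |

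**5. Possible size within an arm (illustration).** The documents give neither the shift caused by the lead-in nor the correlation between visits; both are assumptions. Suppose there is no treatment effect, the lead-in shifts the Day 1 score by s SDs, the SD is equal at both visits, the correlation is rho, and n = 20. A paired t-test stands in for the within-treatment GEE contrast.

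Standardised change: dz = s / √(2(1 − rho)). Noncentrality: dz × √20. The critical value is 2.093 on 19 df. For example, s = 0.2 and rho = 0.6 give dz = 0.2 / √0.8 = 0.224 and noncentrality 1.00.

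| Assumed shift (SD) | Significant, rho 0.6 | Significant, rho 0.8 |
|---|---|---|
| 0.05 | 5.6% | 6.3% |
| 0.1 | 7.6% | 10.3% |
| 0.2 | 15.8% | 26.9% |
| 0.3 | 29.7% | 52.1% |
| 0.4 | 47.6% | 76.5% |

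The test is two-sided, so these rates are the same whichever way the shift runs.

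**6. Between arms.** A shift common to both arms cancels in the difference of changes. In simulation with 20 per arm, and a common shift of 0.3 or 0.5 SD of the change score, the between-arm test rejected in 5.1% of trials in each case.

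**The case against.** The strongest reply is that the trial is randomized and sham-controlled. Both arms have the same lead-in at each visit, so the treatment comparison is protected. Within-arm change is already open to practice, placebo response and regression to the mean, and the sham arm is there to deal with these. This stands, and it is why the point is a cheap improvement rather than a threat to the main result. It does not remove the point, because XI.1 plans within-treatment tests and the hypotheses are worded as improvement.

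The size is also assumed. A small shift hardly matters: 0.05 SD gives about 6%. A missing rest interval does not prove that there will be no rest. The weaker leg also rests while the stronger leg is tested. All of this stands, so the percentages only illustrate.

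Three stronger readings are tempting, and the documents do not support them:
- *Both arms will look less fatigable at follow-up.* No index is defined. If it is decline from the opening repetitions, prior effort could lower the starting torque and shrink the decline on Day 1, which would run against the hypothesis. A few maximal contractions could also act as a warm-up.
- *Strength testing is absent at every later visit.* This is stated for Day 5 only.
- *The arm comparison loses precision.* Unequal carry-over between subjects could do this, but nothing in the plan allows it to be quantified.

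**Conclusion.** The point holds as a matter of standardisation. Day 1 and Day 5 fatigability are measured after different prior effort, so within-arm change between them cannot be read as change in fatigability alone. This rests on the explicit Day 5 omission and on the inferred Day 1 order.

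The sign and size of the distortion are unknown. Over assumed shifts of 0.1 to 0.4 SD, with 20 subjects and no treatment effect, a within-arm test is significant in about 8% to 48% of trials at rho 0.6 and 10% to 77% at rho 0.8, against a nominal 5%. The upper end needs both the largest shift and the higher correlation.

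The tDCS-versus-sham contrast is not biased, and the sample size is unaffected. At 3 and 6 weeks the problem depends on which battery is meant. Without strength testing, those visits differ from Day 1 as Day 5 does. With it, they match Day 1 and differ from Day 5.

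**What to change.** Amend VII.E.6 as follows:

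1. Use the same lead-in at every fatigability assessment: before the fatigue test on Day 5 and at 3 and 6 weeks, the same short set of contractions and the same fixed rest as on Day 1. A partial remedy is a fixed recovery period between strength and fatigue testing on Day 1 alone. It reduces carry-over but leaves the lead-ins different.
2. State the Day 1 order and the rest interval, and add both tests to the numbered Day 1 list.
3. State which battery applies at 3 and 6 weeks.
4. Define the fatigability index.

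In XI.1, state that the conclusion on leg fatigability rests on the between-arm contrast, with within-arm change as description.

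The cost is a procedure amendment, a few extra minutes per visit and slightly more subject effort. The sample size does not change.
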